5.3. Method of Assignment to Treatment

Patients who meet all criteria for enrollment will be assigned to receive LY3076226. Before each patient's enrollment into the study, an eligibility check must be conducted between the investigational site and the Eli Lilly and Company (Lilly) clinical research personnel to confirm that each patient meets all enrollment criteria. Upon confirmation of eligibility, the sponsor will confirm the dose, identification number, and cohort assignment for each patient. No dose escalations (that is, to the next cohort) can occur without prior discussion and agreement with the responsible Lilly Clinical Research Physician/Clinical Research Scientist (CRP/CRS).

If investigators have eligible patients who have consented concurrently, more than 1 or 3 patients may be entered at a particular dose level (or 6 if the cohort has been expanded due to a DLT) provided that accrual has not ceased due to excessive toxicity. This enrollment procedure is allowed because of the advanced disease state of this patient population and the screening involved in defining eligibility. This event should be approved by the sponsor following discussions with the investigators.

6. A Priori Statistical Methods

6.1. General Considerations

Statistical analysis of this study will be the responsibility of Eli Lilly and Company. The interpretation of the study results will be the responsibility of the investigator with the Lilly CRP/CRS, pharmacokineticist, and statistician. The CRP/CRS and statistician will also be responsible for the appropriate conduct of an internal review for both the final study report and any study-related material to be authorized by Lilly for publication.

The analyses for this study will be descriptive; no p-values will be calculated. Data analyses will be provided by cohort and overall whenever appropriate. For continuous variables, summary statistics will include number of patients, mean, median, standard deviation, standard error, minimum, and maximum. Categorical endpoints will be summarized using number of patients, frequency, percentages, and their standard errors. Exploratory analyses of the data that are not described in the protocol will be conducted as deemed appropriate.

Any change to the data analysis methods described in the protocol will require an amendment ONLY if it changes a principal feather of the protocol. Any other change to the data analysis methods described in the protocol and the justification for making the change will be described in the clinical study report (CSR).

The following data handling conventions will be used in the analysis (see [Table JOBA.6.1](#)).

Table JOBA.6.1. Data Handling Conventions

Term	Definition or Rule
Relative Study Day	
If assessment is on or after date of first dose then $(\text{date of assessment}) - (\text{date of first study drug dose}) + 1$
 
If assessment precedes first dose of drug then $(\text{date of assessment}) - (\text{date of first study drug dose})$
 
There is no Study Day 0. Study Day 1 is the date of first dose and study day -1 is the day before the first dose.

Baseline	
For change from baseline analyses, baseline value is defined as the last reported measure on or before the first dose date (prior to the dose administration), unless otherwise specified.
 
For change from baseline within a cycle, baseline value is defined as the measure prior to the first dose of that cycle, unless otherwise specified.
 
If more than one pre-dose measures are available, they may be averaged if appropriate.

Entered	Patients who have signed the informed consent document (ICD).
Enrolled	Patients who have been assigned to a study treatment and have received at least one dose of study treatment.

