7.2.2.3. Dose-Escalation Method

For Part A, the proposed starting dose level will be 0.2 mg/kg. Dose escalation will proceed at a maximum dose increment of 100%. An accelerated dose-escalation scheme will be used, as follows: initial cohorts will enroll at least one patient each until a dose level of 1.6 mg/kg is reached, unless a \geq Grade 2 toxicity that is at least possibly related to LY3076226 is observed requiring additional patients to be enrolled to a dose level. After which a modified 3+3 scheme, with incorporation of a Bayesian model-based, toxicity-band method (Neuenschwander et al. 2008), will be followed, wherein at least 3 patients will be enrolled in each of the subsequent cohorts. The Bayesian model-based, toxicity-band method incorporates the prior expectations of the dose-toxicity curve and the observed DLT data after each cohort and provides quantitative guidance on the determination of the dose level for the next cohort, with control of overdosing probability. This method will be applied to the observed data on an ongoing basis throughout the dose escalation. The toxicity-band method will stop if the prespecified maximum number of patients is reached or the recommended next dose level has been administered to at least 6 patients.

During the dose-escalation period, the investigators and Lilly CRP/CRS will consider both the model recommendation and the observed DLT rate at each cohort to determine the next dose level and determine when to stop dose escalation. Safety data, in particular, AEs, will be the primary criteria for dose escalation. In addition, if available at the time of the dose-escalation decision, PK (C_{max} , AUC, and systemic clearance [CL]) results will be used as secondary/supporting data for dose escalation. Additional patients may, therefore, be enrolled at a specific dose level to characterize PK/PD. No dose escalation can occur without prior discussion and agreement between the investigator and the Lilly CRP/CRS; the decision will be documented in writing. Inpatient dose escalations are not permitted.

The example dose levels for Part A are shown in [Table JOBA.3](#). Intermediate or higher dose levels may be explored, if deemed necessary, after discussion between the Lilly CRP/CRS and investigators. The toxicity-band method has the ability to accommodate additional dose levels naturally.

Details regarding the toxicity-band method for this study are provided in [Attachment 10](#).

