5.1. Summary of Study Design

Study JOBA is a multicenter, outpatient, nonrandomized, open-label, dose-escalation Phase 1 study of intravenous (IV) LY3076226 in patients with advanced or metastatic cancer. Eligible patients will receive LY3076226 as an IV infusion on Day 1 of a 21-day cycle.

Dose escalation for LY3076226 in Part A will be driven by an accelerated dose-escalation scheme. The initial dose levels will enroll one patient per cohort. A modified 3+3 dose-escalation scheme will be followed in subsequent cohorts, with incorporation of a Bayesian model-based dose-escalation method (Neuenschwander et al. 2008). For more details, please refer to Protocol Section 6.2 and 7.2.2.

Once MTD is identified in Part A, up to approximately 15 patients who have known alterations of FGFR3 will be enrolled in each of Parts B (urothelial carcinoma) and C (other malignancies) to further evaluate the safety profile of LY3076226, characterize the exploratory biomarker assays, and document any antitumor activity.

[Figure JOBA.5.1](#) is a representative illustration of Study JOBA study design, showing the dose escalation design in advanced cancer (Part A) and MTD expansions Parts B and C.

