5.2. Determination of Sample Size

To determine the recommended Phase 2 dose of LY3076226, an adequate sample size is required. A sufficient sample size will allow for an accurate evaluation of the relationship between exposure and toxicity, as well as an evaluation of the relationship between exposure and pharmacological effects using descriptive statistics and appropriate modeling techniques, if data warrant.

The actual sample size of Part A will primarily be determined by the observed toxicity and the incidence of DLTs. Under the modified 3+3 dose-escalation scheme, each cohort will include 3 to 6 patients. The anticipated sample size for Part A ranges from approximately 20 to 35 patients, depending on the observed toxicity. Each of Parts B and C expansion cohorts will enroll up to approximately 15 patients. The overall sample size is thus estimated to be approximately 65 patients.

[figure not shown]

Figure JOBA.5.1. Illustration of Study JOBA study design.

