6.8.2. Dose Limiting Toxicity

Dose limiting toxicities (DLTs) will be summarized and listed by cohort and overall for the safety population.

Dose-equivalent toxicities (DETs) will also be summarized and listed by cohort and overall for the safety population.

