6.12. Efficacy Analyses

The study is not designed to make an efficacy assessment. However, any tumor response data will be listed and summarized. Particularly, the antitumor effect will be summarized by the overall response rate (ORR, defined by the total number of responses divided by the number of patients on therapy) and disease control rate (defined by the total number of stable disease + responses divided by the number of patients on therapy) by cohort and overall. Mean, median, range, and exact 90% confidence intervals (CI) will be provided. A patient is considered to have a tumor response if they achieve a confirmed complete response (CR) or partial response (PR) according to RECIST 1.1 or lymphoma criteria (Cheson et al. 2007) or a confirmed stringent complete response (sCR), CR, very good partial response (VGPR) or PR according to multiple myeloma (IMWG) criteria (Rajkumar et al, 2011). Reported lesion measurement data, including sum of target lesions, change and/or percent change from baseline sum at each visit will be listed for all patients on therapy. Investigator-determined response by cycle will be listed.

Time-to-event variables, such as progression-free survival (PFS) and duration of response, will be listed and summarized. PFS time is defined as the time from the first dose of the study drug to progressive disease (PD, either due to objective progressive disease or symptomatic deterioration) or death due to any cause, occurring without observed disease progression. Duration of response (DoR) is defined as the time from the first assessment of any tumor response to PD or death due to any cause, occurring without observed disease progression. Patients not known to have progressed or died while on study will have their PFS and DoR time censored at the date of the last objective progression-free disease assessment. Patients for whom there is no record of progression, death, or post baseline radiographic assessment will have their PFS time censored on the day of first dose of any study drug. The Kaplan-Meier method (Kaplan and Meier 1958) will be used to estimate the survival curves, medians with 90% CI, and PFS rates at various time points if applicable. For Part C, time-to-event variables may be summarized by different tumor types if the data warrant.

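### The standard error is the only precision measure planned for DLT and adverse event percentages by cohort, and it is zero whenever no patient or every patient has the event

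*SAP*

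**What the plan says.** The general rule in SAP 6.1 is "Categorical endpoints will be summarized using number of patients, frequency, percentages, and their standard errors", and Protocol 10.1 has an identical sentence. SAP 6.1 also sets the level of reporting: "Data analyses will be provided by cohort and overall whenever appropriate". Neither document gives a formula for the SE, or a rule for percentages of 0% or 100% or for a cohort of one.

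The cohorts are small. For the start of Part A, SAP 5.1 says "The initial dose levels will enroll one patient per cohort"; Protocol 7.2.2.3 is slightly looser: "initial cohorts will enroll at least one patient each until a dose level of 1.6 mg/kg is reached". For the modified 3+3 stage, SAP 5.2 says "each cohort will include 3 to 6 patients". For the expansions it says "Each of Parts B and C expansion cohorts will enroll up to approximately 15 patients".

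For safety, SAP 6.8.2 says "Dose limiting toxicities (DLTs) will be summarized and listed by cohort and overall for the safety population". It treats what it calls dose-equivalent toxicities in the same way; I read these as the DLT-equivalent toxicities of Protocol 7.2.2.2. Neither SAP 6.8.2 nor SAP 6.8.3 (adverse events) specifies an interval.

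For response the plan differs. SAP 6.12 says of the overall response rate and the disease control rate: "Mean, median, range, and exact 90% confidence intervals (CI) will be provided". Protocol 10.8 also plans an exact 90% interval for the response rate.

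**The concern.** The usual SE of a proportion collapses to zero at the boundary. A cohort in which nobody has the event gets an SE of 0, whether it holds one patient or fifteen. Printed beside a percentage, that reads as no uncertainty, and the SE cannot tell a dose tried in one patient from a dose tried in fifteen.

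The primary objective is a dose that can be given safely, and the study is stated not to be designed to assess efficacy. Yet the measure that works at the boundary (the exact interval) is assigned to response, and the one that fails there is assigned to toxicity. At stake is whether a reader of the safety tables is told how little a clean small cohort rules out.

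**Working it through.** **Inputs.** Cohort sizes of 1, 3 to 6 and about 15 come from SAP 5.1 and 5.2. The 90% level and the exact method are those of SAP 6.12. The documents state no SE value, so there is no figure to reproduce. The true event rates below are assumptions, shown as a range; 20% and 33% are the edges of the targeted toxicity band in Protocol Attachment 10.

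**Step 1: the SE.** SE = sqrt(p(1-p)/n), with p the observed proportion. At p = 0 or p = 1 the product p(1-p) is 0, so SE = 0 at every n. At n = 1 the observed proportion can only be 0 or 1, so SE is always 0. Dividing by n-1 instead does not help: the SE is then undefined at n = 1 and still 0 at 0/n and n/n for larger n. One event changes the picture abruptly: 1/6 gives sqrt((1/6)(5/6)/6) = 15.2 percentage points, against 0 for 0/6.

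**Step 2: the exact interval for the same data.** For 0/n, the upper limit of the two-sided 90% Clopper-Pearson interval is 1 - 0.05^(1/n).

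| Observed | Printed under the plan | Exact 90% interval |
|---|---|---|
| 0/1 | 0% (SE 0) | 0 to 95.0% |
| 0/3 | 0% (SE 0) | 0 to 63.2% |
| 0/6 | 0% (SE 0) | 0 to 39.3% |
| 0/15 | 0% (SE 0) | 0 to 18.1% |

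The mirror results behave the same way: 3/3 prints 100% (SE 0), with an exact interval of 36.8% to 100%.

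**Step 3: how often this happens.** For a true rate q, the chance of a zero SE is q^n + (1-q)^n. For q = 10% and n = 3 this is 0.001 + 0.729 = 0.730.

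| Assumed true rate | n = 1 | n = 3 | n = 6 | n = 15 |
|---|---|---|---|---|
| 5% | 100% | 86% | 74% | 46% |
| 10% | 100% | 73% | 53% | 21% |
| 20% | 100% | 52% | 26% | 3.5% |
| 33% | 100% | 34% | 9% | 0.2% |

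The problem is therefore routine for uncommon events in Part A cohorts. It becomes infrequent as the cohort or the event rate grows.

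**The case against.** The strongest reply is that nothing depends on this SE. Escalation uses the toxicity-band posterior, with doses excluded when the posterior probability of overdosing exceeds 0.25 (Protocol Attachment 10), together with safety review and the observed DLT rate (Protocol 7.2.2.3). Parts B and C use a count rule, one third or more of at least 6 patients (Protocol 7.2.3). The RP2D is agreed from safety, PK and PD data and may not exceed the MTD (Protocol 7.2.4). All of this stands. A reader might infer that these SEs are the error bars on which dose decisions rest; the documents do not support that.

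Four other inferences also go too far.

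- **That every table is affected.** The response and disease control tables carry exact 90% intervals as well.
- **That a reader sees only 0% (SE 0).** The same sentence requires the number of patients and the frequency, and DLTs are also listed.
- **That zero events is the usual result in cohorts of 3 to 6.** Zero is the single most likely count only when the true rate is below 1/(n+1), which is 25% at n = 3 and about 14% at n = 6. At a 20% rate, 0/6 has probability 26% and 1/6 has 39%. Nor is a zero SE confined to the smallest cells: it also occurs at 0/65.
- **That the plan implies impossible limits.** One can build a normal interval from 1/6, 16.7% ± 1.645 × 15.2 points, which runs from about -8% to 42%. Neither document plans such an interval; the intervals they specify for rates are exact.

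The plan also leaves some latitude. Cohort summaries are given where appropriate, so an SE for a one-patient cohort is not clearly required.

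These points limit the consequence but do not remove the defect. Printing n lets an alert reader discount the SE; it does not make the SE informative. The toxicity-band model covers DLTs, which are Cycle 1 events. No model is specified for DLT-equivalent toxicities from Cycle 2 onward, although Protocol 7.2.2.2 has their rate assessed at interim analyses, with more than 33% as an example of an unacceptable level. A 0/6 result there would print SE 0, while its exact upper limit is 39%.

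**Conclusion.** The point holds as one about reporting. For DLT, DLT-equivalent and adverse event percentages by cohort, the only precision measure specified is exactly zero at 0/n and n/n and in every one-patient cohort. It gives the same value for 0/1 as for 0/15, where the exact 90% upper limits are 95% and 18%.

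The result rests on the usual SE formula, which the documents do not state. The frequencies in 3- and 6-patient cohorts rest on assumed true rates and run from 86% down to 9% across the range shown. No estimate, escalation step, review trigger or RP2D rule changes. The effect is confined to how precisely the safety tables appear to estimate toxicity.

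**What to change.** In SAP 6.1 and 6.8 and in Protocol 10.1, for DLTs, DLT-equivalent toxicities and key adverse events by dose level, replace the SE with the exact (Clopper-Pearson) two-sided 90% confidence interval already planned for the response rate. The SAP should list which adverse events count as key. For other categorical summaries, such as demographics and disposition, report counts and percentages without an SE in very small cohorts, and state the cohort size below which this applies.

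The cost is a change of phrase and a standard procedure call. SAP 6.1 requires a protocol amendment only for a change to a principal feature of the protocol, and lets other analysis changes be described and justified in the clinical study report, so this could be done without one. The downside is that the stated precision will look less favourable: a clean 3-patient dose level would show 0 to 63% instead of an SE of 0.

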6.2. Handling of Dropouts or Missing Data

Missing data, except dates, will not be imputed. Historical data such as historical diagnosis, historical illness, pre-existing conditions and prior therapies should be collected in a sufficiently informative way. For example, in order to be considered as historical illness, events occurring in the same year as study entry should have at least a known month and year for the end date, while events occurring in previous years should have at least a known year for the end date. When dates need to be imputed, missing days will be replaced with 15th of the month and missing day/month with 01 JULY.

Patients who withdraw from the study before receiving study drug will be replaced and will not be included in the safety or efficacy assessments unless the withdrawal is due to a safety issue that is possibly related to study procedure.

In the following situations, patients will be considered non-evaluable and may be replaced to ensure that enough patients complete one cycle of therapy at each dose level, unless accrual to that cohort has stopped due to a DLT:

1. Any patient who is discontinued from the study before completing one cycle of therapy unless they experience a DLT prior to withdrawal.
2. Patients who are not evaluable for PK, but who complete one cycle of therapy.

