8.1.2.2.1. Prior to Administration of Study Drug

During prescreening and screening, all AEs and SAEs (regardless of relatedness to protocol procedures) are collected after the patient has signed the ICF. For patients who do not enroll in the trial (that is, have not received at least one dose of study treatment), only AEs and SAEs related to protocol procedures are required to be collected.

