10.1. General Considerations

Up to approximately 65 patients may be enrolled in this multicenter, nonrandomized, open-label Phase 1 dose-escalation study of LY3076226. Patients will be enrolled into cohorts sequentially without randomization to dose. The Bayesian model-based, toxicity-band method will be followed to assist dose escalation. The toxicity-band method will provide quantitative guidance on the determination of the dose level for the next cohort based on the observed DLT data. Compared with the traditional 3+3 method, the toxicity-band method provides a lower underdosing rate and a higher MTD selection rate, with a well-controlled overdosing rate at a prespecified criterion. Refer to [Attachment 10](#) for more details. The sample size for Part A will primarily be determined by the incidence of DLTs prior to establishing the MTD in Part A. The anticipated sample size for Part A ranges from approximately 20 to 35 patients. In each of Parts B and C, up to approximately 15 patients who have known alterations of FGFR3 will be enrolled. The sample sizes of Parts B and C have been selected to allow adequate assessment of safety at the recommended dose and to characterize the biomarker assay.

Statistical analysis of this study will be the responsibility of Eli Lilly and Company.

The analyses for this study will be descriptive; no p-values will be calculated. Data analyses will be provided by cohorts and for all study patients combined whenever appropriate. For continuous variables, summary statistics will include number of patients, mean, median, standard deviation, standard error, minimum, and maximum. Categorical endpoints will be summarized using number of patients, frequency, percentages, and their standard errors. Missing data will not be imputed.

The interpretation of the study results will be the responsibility of the investigator with the Lilly CRP/CRS, pharmacokineticist, and statistician. The CRP/CRS and statistician will also be responsible for the appropriate conduct of an internal review for both the final study report and any study-related material to be authorized by Lilly for publication.

Exploratory analyses of the data not described in Sections [10.2](#) through [10.9](#) will be conducted as deemed appropriate.

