Attachment 1. Protocol JOBA Study Schedule

Baseline Assessments

Relative day to Cycle 1, Day 1	Pre-screening	Screening			Comments
		≤28	≤14	≤7	
Informed consent	X	X			ICF signed (prior to performance of any protocol-specific tests/procedures). Prescreening consent for Parts B and C only, for patients with unknown FGFR3 alteration status.
Collection of tumor tissue sample for local FGFR3 alteration testing for eligibility (Parts B and C only)	X				Archived tissue or biopsy if archived tissue is not available. If prescreening biopsy is performed and results are positive and patient signs study ICF, a portion of this biopsy may be used for pretreatment biopsy for the study.
Radiological tumor assessment according to RECIST 1.1			X		Radiological assessments obtained previously (≤28 d prior to C1D1) as part of routine clinical care may be used as the baseline assessment. Appropriate tumor assessment criteria should be used for patients with multiple myeloma (IMWG [Rajkumar et al. 2011; refer to Attachment 5]) or lymphoma (Cheson et al. 2014).
Medical history			X		Including alcohol/tobacco use and other relevant habits assessments.
Physical examination			X		Including height and weight.
Standard ophthalmic examination			X		Performed by an ophthalmologist.
Vital signs			X		Including temperature, BP, PR, RR.
ECOG performance status			X		
Central ECG			X		One set of triplicate ECGs.
Local hematology			X		Refer to Attachment 2 .
Central serum chemistry			X		Refer to Attachment 2 . Enrollment or dose adjustment decisions may be based upon chemistry results performed at a local laboratory; however, a sample must be sent to the central laboratory.
Coagulation (local)			X		Refer to Attachment 2 .
Local urinalysis			X		
Tumor measurement (palpable or visible)			X		
CTCAE v 4.0 grading (preexisting conditions)			X		Refer to Section 8.1.2 .

Baseline Assessments (continued)

Relative day to Cycle 1, Day 1	Pre-screening	Screening			Comments
		≤28	≤14	≤7	
Concomitant medications			X		
Local tumor markers			X		If applicable.
Central archived tissue sample			X		Collected only if patient has met inclusion/exclusion criteria.
Local pregnancy test, serum				X	For women of childbearing potential.

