6.8.3. Adverse Events

AE terms and severity grades will be assigned by the investigator using CTCAE Version 4.0. In addition, AE verbatim text will also be mapped by the sponsor or designee to corresponding terminology within the Medical Dictionary for Regulatory Activities (MedDRA) dictionary. AEs will be reported using a unified CTCAE/MedDRA reporting process:

- The CTCAE v4.0 term reported by the investigator will be mapped to the MedDRA preferred term (PT) and system organ class (SOC) of the corresponding MedDRA lowest level term (LLT), unless the reported CTCAE term is “Other-specify”.
- If the reported CTCAE term is “Other-specify” the MedDRA LLT, PT and SOC mapped from the verbatim AE term will be used
- All listings and summaries will use the CTCAE terms when available or the MedDRA LLT, along with the MedDRA PT resulting from this process.

A treatment emergent adverse event (TEAE) is defined as any AE that begins on or after the day of the first dose of LY3076226 or any pre-existing condition that increases in CTCAE grade on or after the day of the first dose of LY3076226. Comparisons of pre-existing conditions to treatment events at the LLT level will be used in the treatment-emergent computation.

The number of patients who experienced a TEAE, SAE, or TEAE possibly related to study drug, will be summarized. TEAEs will be summarized by SOC, by PT terms of decreasing frequency within SOC, and by maximum CTCAE grade and grade categories.

Historical illnesses are defined as events which ended before completion of the screening visit. Pre-existing conditions are defined as AEs that begin but do not resolve prior to the first dose of study drug is administered. The pre-existing conditions will be presented by patient and can be combined with the adverse event listing, so that the history of the pre-existing conditions/adverse events can be traced. Historical illnesses and pre-existing conditions will be summarized and listed by cohort and overall for all patients on therapy.

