6.17. Clinical Trial Registry Analyses

Additional analyses will be performed for the purpose of fulfilling the Clinical Trial Registry (CTR) requirements.

Analyses provided for the CTR requirements include the following:

Summary of AEs, provided as a dataset which will be converted to an XML file. Both SAEs and ‘Other’ AEs are summarized by MedDRA preferred term (PT) within treatment group.

- An AE is considered ‘Serious’ whether or not it is a treatment emergent adverse event (TEAE).
- An AE is considered in the ‘Other’ category if it is both a TEAE and is not serious. For each SAE and ‘Other’ AE, for each term and treatment group, the following are provided:
 - the number of participants at risk of an event
 - the number of participants who experienced each event term
 - the number of events experienced.

- Adverse event reporting is consistent with other document disclosures for example, the CSR, manuscripts, and so forth.

A participant flow will be created that will describe how many entered patients completed the study, and for those who did not, the frequency of each reason for not completing. This analysis will be based on study discontinuation, not treatment discontinuation.

7. References

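### The SAP's partial-date rule ignores the first dose date, so AEs with an incomplete onset date can be misclassified as treatment-emergent or not

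*SAP*

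**What the plan says.** SAP 6.2 opens with a general statement: "Missing data, except dates, will not be imputed". It goes on to how completely historical diagnoses, illnesses, pre-existing conditions and prior therapies should be recorded, and ends the paragraph with the rule: "When dates need to be imputed, missing days will be replaced with 15th of the month and missing day/month with 01 JULY". The completeness requirement in that paragraph concerns the end date of historical illness. It does not cover the onset date of an AE.

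SAP 6.8.3 defines a treatment-emergent AE (TEAE) as "any AE that begins on or after the day of the first dose of LY3076226", or a pre-existing condition whose grade rises from that day on. Pre-existing conditions are themselves defined by having begun, and not resolved, before the first dose. Neither SAP 6.8.3 nor Table JOBA.6.1 says how to treat a partial onset date.

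Two outputs visibly use the flag. SAP 6.8.3: "The number of patients who experienced a TEAE, SAE, or TEAE possibly related to study drug, will be summarized", with further TEAE tables by system organ class, preferred term and maximum grade. SAP 6.17 places an AE in the registry's *Other* "category if it is both a TEAE and is not serious".

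Protocol 10.1 differs from the SAP on imputation, stating without exception: "Missing data will not be imputed".

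**The concern.** Treatment-emergent status is a comparison of two dates, and the imputation rule fixes one of them without looking at the other. For an AE in the month of first dose with the day missing, the classification depends only on the day of the month on which the patient was dosed. A first dose on the 16th or later puts every such AE before dosing; a first dose on the 15th or earlier puts every one on or after it.

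An on-treatment AE moved before the first dose leaves the TEAE counts. It also becomes a pre-existing condition, and its grade becomes the level against which later worsening is judged. The opposite error is possible because pre-dose AEs are in the database: under Protocol 8.1.2.2.1, "all AEs and SAEs (regardless of relatedness to protocol procedures) are collected after the patient has signed the ICF".

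Characterising safety is a secondary objective, and tables are given by cohort. The early accelerated cohorts may hold a single patient, so one misplaced event can change a cohort's TEAE profile.

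**Working it through.** The documents give no figure to reproduce. The check applies the SAP 6.2 rule and the SAP 6.8.3 test literally.

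**Examples**

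| First dose | True onset | Recorded as | Imputed | True status | Assigned status |
|---|---|---|---|---|---|
| 20 March | 22 March | March | 15 March | TEAE | not TEAE |
| 10 March | 3 March | March | 15 March | not TEAE | TEAE |
| 5 September | 10 November | year only | 1 July | TEAE | not TEAE |

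**Assumptions (not in the documents).** First dose is equally likely on each of 365 days (seven 31-day months, four of 30 days, one of 28). Onset is equally likely on each day of the window. Windows are Days 1–21 (one cycle; 365 × 21 = 7,665 date pairs), Days 1–63 (three cycles; 365 × 63 = 22,995) and the 28 days before dosing (365 × 28 = 10,220).

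**Day missing, on-treatment onset moved before first dose.** This needs a first dose on the 16th or later and an onset later in the same month. The number of pairs is 136 in a 31-day month (16 × 17 / 2), 120 in a 30-day month (15 × 16 / 2) and 91 in a 28-day month (13 × 14 / 2).
- Total: 7 × 136 + 4 × 120 + 91 = 1,523.
- Days 1–21: 1,523 / 7,665 = 19.9%. Of the 5,145 onsets in the month of first dose: 1,523 / 5,145 = 29.6%.
- Days 1–63: the same 1,523 pairs, so 1,523 / 22,995 = 6.6%.

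**Day missing, pre-dose onset moved to on or after first dose.** This needs a first dose on the 1st to 15th and an onset earlier in that month: 0 + 1 + … + 14 = 105 pairs per month. 12 × 105 = 1,260, and 1,260 / 10,220 = 12.3%.

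**Day and month missing.** 1 July is day 182 of the year.
- On-treatment onsets lost need a first dose on days 183–365 and an onset in the same year. Days 1–21: 163 × 21 + (20 + 19 + … + 1) = 3,423 + 210 = 3,633, and 3,633 / 7,665 = 47.4%. Days 1–63: 121 × 63 + (62 + 61 + … + 1) = 7,623 + 1,953 = 9,576, and 9,576 / 22,995 = 41.6%.
- Pre-dose onsets gained need a first dose on days 1–182 and an onset in the same year: (0 + 1 + … + 28) + 153 × 28 = 406 + 4,284 = 4,690, and 4,690 / 10,220 = 45.9%.

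**Effect on all Cycle 1 AEs.** If 1–10% of onset dates lack the day (assumption): 0.199 × 1% = 0.2% to 0.199 × 10% = 2.0% lose TEAE status. Over 63 days: 0.066 × 1% = 0.07% to 0.066 × 10% = 0.7%.

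**Under the anchored rule (see the fix), before its exception.** On-treatment onsets lost: 0 in every setting, because an onset in a later month or year is imputed after the first dose anyway. Pre-dose onsets counted as TEAE become:
- day missing: 7 × 462 + 4 × 434 + 378 = 5,348, and 5,348 / 10,220 = 52.3%;
- day and month missing: 406 + 336 × 28 = 9,814, and 9,814 / 10,220 = 96.0%.

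The 462, 434 and 378 are the pre-dose days falling in the dosing month, capped at 28 per dose date, for months of 31, 30 and 28 days.

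**The case against.** **Scope.** The imputation sentence closes a paragraph mainly about historical data and never mentions AE onset, so it may not have been meant for AEs. That reading is possible. But the opening exception for dates is general, and on the narrow reading AE onset has no rule at all. Protocol 10.1 points the same way, since it allows no imputation. Either way the classification of a partial onset date needs a sentence in the SAP.

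**Other records.** Pre-existing conditions are graded at screening, sites record changes and new AEs on study, and SAP 6.8.3 compares the two at lowest-level-term level. These records could often reveal the true order. The SAP does not say that they override an imputed date.

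**Realism.** Cycle 1 has visits on Days 1, 2, 4, 8 and 15, several DLT criteria need day-level durations, and CRF data are reviewed. An onset known only by year so close to dosing is unlikely. This stands: the 40–50% figures describe rare records. In addition, TEAE tables count patients, so a lost event removes a patient from a row only if no other qualifying event of that term remains. That attenuation is not quantified here.

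**The remedy has its own error.** With equal onset density over 28 days before and 63 days after dosing, day missing and no exception, total misclassification rises from (1,523 + 1,260) / 33,215 = 8.4% to 5,348 / 33,215 = 16.1%. Post-dose density must exceed pre-dose density by (5,348 − 1,260) / 1,523 = 2.7-fold before total error falls. This also stands, and it is why the exception is an essential part of the change.

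**Conclusion.** The concern holds. As written, the rule misclassifies some AEs with partial onset dates in both directions, and nothing in either document ties an imputed AE onset to the first dose.

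The likely size is small. The percentages apply only to AEs with incomplete onset dates, rest on uniform calendar dates, and depend on a partial-date rate that the documents do not give. The net direction is unknown, because it depends on how partial dates split before and after dosing.

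The effect is confined to the TEAE tables, the possibly-related TEAE counts and the registry's *Other* category. DLT summaries, cohort reviews, listings of SAEs, deaths and discontinuations, and registry SAEs do not visibly use the flag. A misplaced on-treatment event remains visible among the pre-existing conditions, and later worsening in grade still makes it a TEAE. The change should be made because the error is avoidable, cheap to prevent and can remove on-treatment events from the safety tables; it does not threaten the dose recommendation.

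**What to change.** Add to SAP 6.2:
- For AE onset, when the known part of the date matches the month (or, if the month is missing, the year) of first dose, use the later of the rule date and the first dose date.
- Exception: do not do so when the AE end date, its record as a pre-existing condition at screening, or other CRF information shows that onset preceded dosing.
- An imputed end date may not precede onset.
- Keep the 15th and 1 July for historical diagnoses and prior therapy.

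The SAP should also acknowledge that it departs from Protocol 10.1 in imputing dates.

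The cost is two or three sentences for the AE rule and a few lines of derivation code, with no new data. The downside is that more pre-dose AEs with ambiguous dates count as treatment-emergent: before the exception is applied, up to 52.3% of 28-day pre-dose onsets with the day missing (12.3% now) and up to 96.0% with day and month missing (45.9% now). In return, no on-treatment onset is moved before the first dose by imputation. That is the conservative direction for safety reporting, and the exception limits the over-attribution.
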